Statistical Methodology	
The primary efficacy analysis for temperature maintenance will be based on the evaluable population of subjects who achieve normothermia by 4 hours and continue cooling treatment with the COOLSTAT System.
 
The proportion of subjects fulfilling success criteria and 90% confidence intervals will be reported and compared to the a priori minimum acceptable criteria:
 
 • at least 75% of the subjects will reach normothermia (core temperature $\leq 37.5^{\circ}\text{C}$) within 4 hours of starting COOLSTAT cooling, and • at least 75% of the subjects' core temperatures remain between 36°C and 37.5°C for 80% of the steady state time following the initial achievement of 37.5°C. 
All adverse events (AEs) reported during the study will be presented in tabular format to include: time of onset, whether or not the patient continued in the study, the nature of intervention and resolution. The potential contribution to the AE by the device will be assessed by the attending physician who reports the AE and the investigator.

Data Safety Monitoring Board	
A DSMB will be formed to monitor this study. The DSMB will meet: 1) before any subjects are enrolled (to review the study), 2) after the first 5 subjects (all with ICP monitoring), 3) after the first 10 subjects (before proceeding to 24-hour

upon being reconnected to the CoolStat is $\leq 37.5^{\circ}\text{C}$. If the subject's temperature is $> 37.5^{\circ}\text{C}$ upon being reconnected to the device, the device will be given up to an additional 4 hour-period to bring the patient to normothermia ($\leq 37.5^{\circ}\text{C}$). Once the subject's core temperature is $\leq 37.5^{\circ}\text{C}$, the device will be considered in steady state.

cooling treatment), 4) after each 6-month period of study, 5) at the end of the study, and 6) after any serious adverse event.

A clinical monitor will also be used to periodically visit the study sites and monitor the activities of the study to ensure that the study protocol, consent activities and data collection are being completed in accordance with specified procedures.

The Clinical Monitor and DSMB will be comprised of:

- [name] - Clinical Monitor
- [name] (Johns Hopkins) - Chair of DSMB - Voting Member
- [name] (Johns Hopkins) - DSMB Voting Member
- [name] (UMMC) - DSMB Voting Member
- [name] (UMMC) - DSMB Voting Member
- [name] (UMMC) - PI (Non-Voting Member)

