6.6 Sample size calculations

The sample size was determined from the calculation below, using the following assumptions:

$$n = \left[\frac{z_{\alpha} \sqrt{p_0(1-p_0)} + z_{\beta} \sqrt{p_1(1-p_1)}}{p_1 - p_0} \right]^2$$

n: minimum sample size

$p_0 = 0.9$ Assumed proportion of subjects successfully cooled

$p_1 = 0.75$ Lowest acceptable proportion of subjects successfully cooled

$\delta = |p_1 - p_0| = 0.15$ Difference between ideal and minimum acceptable

Confidence (α): 90%

$$z_{95} = 1.28$$

Statistical Power (β): 80%

$$z_{80} = 0.84$$

n = 25 subjects completing treatment, therefore a sample size of 30 subjects was selected to allow for dropouts. The study will enroll up to 70 subjects, accounting for a 55% expected post-consent screen failure rate. Enrollment will stop once the 30th subject receives COOLSTAT therapy.

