Similarly, per standard of care in the NCCU, a maximum allowed limit will be imposed for a sustained increase in ICP >5 minutes above max threshold despite standard of care intervention (using existing max institutional limits for the indication being treated). In this event, COOLSTAT use will be discontinued for that subject. Once the COOLSTAT is discontinued due to ICP elevation, it will not be restarted for that subject. However, the study team will continue to monitor ICP to see if it recovers back to baseline value after the COOLSTAT is turned off. The Investigator or their designee must complete an Adverse Event form detailing the event and the value of the ICP prior to, during and after the COOLSTAT was used. See Section 10.0 on procedures following the occurrence of an Adverse Event.

The Investigator or their designee will perform an initial cooling assessment 4 hours after COOLSTAT cooling has begun to determine if the subject has reached normothermia (≤ 37.5 C) sometime within the 4-hour cooling period. Starting from the initiation of normothermia, a subject's core temperature may fluctuate (within about 36.0-37.5 C), but

Transnasal Induction of Normotherapy in NCCU Fever Patients

if the core temperature $>39.0^{\circ}\text{C}$ for 4 hours, CoolStat treatment will be stopped and the subject will be switched to an alternative cooling method. If normothermia ($\leq 37.5^{\circ}\text{C}$) is not achieved within the 4-hour period, the Investigator or their designee will remove the subject from the COOLSTAT device. The subject will be classified as a treatment failure and placed on standard of care treatment at the discretion of the Investigator or their designee and manual data collection will continue per the instructions for Phase 2 in Section 9.4. NOTE – if the Investigator feels that the subject's temperature is approaching the target and the subject is being adequately cooled, CoolStat device operation can be allowed to continue beyond the 4-hour period. The Investigator should note if this is the case in the CRF.

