13.0 Statistical Analysis Plan

The primary efficacy analysis for cooling performance will be based on the evaluable populations of subjects who undergo cooling treatment with the COOLSTAT System. Analysis will be performed on treatment initiated and treatment completed populations. Subjects who achieve normothermia (core temperature $\leq 37.5^{\circ}\text{C}$) within 4 hours of starting COOLSTAT treatment and maintain normothermia for the duration of the treatment will be determined to have been treated successfully.

The primary efficacy analysis for temperature maintenance will be based on the evaluable population of subjects who maintain normothermia (core temperature between 36°C and 37.5°C) for at least 80% of the time following the initial achievement of 37°C will be determined to have been treated successfully.

The proportion of subjects fulfilling success criteria and 90% confidence intervals will be reported and compared to the a priori minimum acceptable criteria:

- at least 75% of the subjects will reach normothermia (core temperature $\leq 37.5^{\circ}\text{C}$) within 4 hours of starting COOLSTAT cooling, and
- at least 75% of the subjects' core temperatures remain between 36°C and 37.5°C for 80% of the steady state time following the initial achievement of 37.5°C .

Continuous measurements will be summarized using the mean and standard deviation. Categorical variables will be reported using percentages and confidence intervals. Data collected will be plotted to demonstrate the change in core temperature from baseline.

An exploratory analysis of participant subgroups will be performed, stratified by stroke presentation (ischemic versus hemorrhagic). Cooling performance and AEs will be evaluated by subgroup.

Double nostril air flow and single nostril air flow subjects will not be merged or directly compared. The results from subjects treated with single nostril flow will be analyzed separately from subjects treated with double nostril air flow.

Subjects 1 through 20 will be assigned to the double nostril air flow treatment group:

- Subjects 1 through 10 will be treated for 8 hours (N=10)
- Subjects 11 through 20 will be treated for 24 hours (N=10)

Subjects 21 through 30 will be assigned to the single nostril air flow treatment group

- Subjects 21 through 30 will be treated for 24 hours (N=10).
- Subjects 21 through 30 will be treated using a dose escalation model:
 - Dosing for this cohort (flow rate) will begin at 30 LPM.

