 - The dose will be increased by 10 LPM if 3 consecutive subjects complete the study protocol with no serious adverse events (as listed in section 10.5) or unanticipated adverse device events.
 - Up to three doses will be evaluated in this cohort (30 LPM, 40 LPM, 50 LPM).
- The purpose of this cohort is to assess the safety of and optimal dose for the single nostril air flow configuration of the CoolStat.
- Each subject will be examined for adverse events, serious adverse events, and unanticipated adverse device events by an intensivist or otolaryngologist within 24 hours of completing CoolStat therapy.
- Each flow rate cohort must be evaluated by an intensivist or otolaryngologist prior to advancing the protocol to the next increased flow rate cohort.

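### Section 6.6 claims 80% power from 25 completers, but section 13.0 splits the 30 treated subjects 20/10 and bars merging them, so no permitted analysis can exceed 20

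*Combined protocol and SAP*

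**What the plan says.** Section 6.6 sizes a single sample. Its inputs are an assumed success proportion of 0.90, a lowest acceptable proportion of 0.75, z-values of 1.28 and 0.84, and 80% power. It concludes: "n = 25 subjects completing treatment, therefore a sample size of 30 subjects was selected to allow for dropouts". Enrolment ends when the 30th subject has been treated.

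Section 13.0 divides those 30. "Subjects 1 through 20 will be assigned to the double nostril air flow treatment group" (ten treated for 8 hours, ten for 24 hours). "Subjects 21 through 30 will be assigned to the single nostril air flow treatment group", under a flow-rate escalation. It then states: "Double nostril air flow and single nostril air flow subjects will not be merged or directly compared". The single-nostril results are to be analysed on their own, and of that cohort the section says: "The purpose of this cohort is to assess the safety of and optimal dose for the single nostril air flow configuration of the CoolStat".

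The 75% criteria in sections 1.0, 6.3, 13.0 and 13.1 refer to the subjects in general and name neither flow configuration.

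On analysis populations, section 13.0 says of cooling performance: "Analysis will be performed on treatment initiated and treatment completed populations". For maintenance, section 1.0 uses the "evaluable population of subjects who achieve normothermia by 4 hours and continue cooling treatment with the COOLSTAT System". Section 9.3 says of a subject taken off the device for not reaching normothermia within 4 hours: "The subject will be classified as a treatment failure and placed on standard of care treatment".

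**The concern.** The calculation in section 6.6 works only if the 30 treated subjects form one sample. Section 13.0 forbids that, and no other section re-sizes either group. The revision table credits the nostril-assignment criteria to Revision C and the escalation in subjects 21 to 30 to Revision D, and neither entry mentions the sample size. The likely origin is that section 6.6 was not updated. The contradiction itself stands in current text and does not depend on that history.

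At stake is what a reader may credit to the study. Anyone relying on section 6.6 would expect 25 completers and 80% power behind the 75% comparison, and no analysis allowed by section 13.0 provides either. It is also unclear whether the 75% criteria are judged on the 20, on the 10, or on each separately.

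**Working it through.** **Inputs.** From section 6.6: 0.90, 0.75, difference 0.15, z = 1.28 and 0.84, 25 completers, 30 treated. From section 13.0: 20 double-nostril, 10 single-nostril, no merging, 90% intervals. From section 6.3: success if at least 75% meet the criterion.

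**Step 1. Reproduce the plan's figure.** With √(0.9×0.1) = 0.3 and √(0.75×0.25) = 0.4330:

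n = [(1.28×0.3 + 0.84×0.4330)/0.15]² = 24.85, so 25. The stated figure reproduces.

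**Step 2. Largest permitted denominator.** The groups are 20 and 10 and may not be merged, so the maximum is 20. This already pools the 8-hour and 24-hour double-nostril subjects, which the documents do not forbid. A subject removed at 4 hours counts as a treatment failure and stays in the treatment-initiated set, so 20 is attainable for cooling performance. It is still 5 short of 25.

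**Step 3. Power, stated requirement versus best available size.**

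- Printed formula solved for power, Φ[(0.15√n − 1.28×0.3)/0.4330]: n = 25 gives Φ(0.845) = 80.1%; n = 20 gives Φ(0.662) = 74.6%.
- Normal approximation with 0.75 as the null, Φ[(0.15√n − 1.28×0.4330)/0.3]: 74.3% at 25; 65.1% at 20.
- Exact binomial, null 0.75, one-sided level at most 0.10, truth 0.90: at 25, at least 22 successes (actual level 0.096), power 76.4%; at 20, at least 18 successes (actual level 0.091), power 67.7%.

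With 0.75 as the null, even 25 subjects fall short of 80%. That is a separate feature of section 6.6 and not a result of the split.

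**Step 4. Like for like.** The 25 counts completers and the 20 counts treated subjects. Comparing treated with treated, 30 versus 20, the printed formula gives Φ(1.011) = 84.4% and 74.6%. For completers, section 6.6 states no dropout rate; 25 from 30 implies a loss of 5/30. If that loss applied in proportion (an assumption), 20×25/30 = 16.7, about 17 double-nostril subjects would complete, and the printed formula gives Φ(0.541) = 70.6%.

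**Step 5. The success rule itself.** With a true rate of 0.90, the chance that the observed proportion is at least 75% is P(X ≥ 19 of 25) = 99.1% and P(X ≥ 15 of 20) = 98.9%.

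**Step 6. Precision (exact Clopper-Pearson 90% intervals).**

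| Observed | Limits | Width |
|---|---|---|
| 20/25 | 0.625 to 0.918 | 0.29 |
| 16/20 | 0.599 to 0.929 | 0.33 |
| 8/10 | 0.493 to 0.963 | 0.47 |
| 22/25 | 0.718 to 0.966 | 0.25 |
| 18/20 | 0.717 to 0.982 | 0.26 |

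At an observed 80% the interval widens from 0.29 to 0.33 between 25 and 20 subjects. Near 90% the change is small.

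**The case against.** The strongest defence is that this is a feasibility study, called exploratory in section 6.8, whose success rule is an observed 75%. Step 5 shows the chance of meeting that rule is almost the same at 20 as at 25, so no decision turns on the error. That stands, and it limits the consequence. It does not rescue the text: the plan prints a sample size and 80% power for a stated hypothesis, and its own analysis rules cannot deliver them.

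A second defence is that the single-nostril cohort exists for safety and dose, so the criteria were never meant for it. That reading is natural, but it confirms that those ten cannot supply the missing subjects.

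Three stronger readings are tempting and are not supported:

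- A reader might take the 5.5-point fall (80.1% to 74.6%) as the effect of the split. It is not, because 25 is a completer requirement and 20 a treated count; step 4 gives the like-for-like figures.
- A reader might extend the power loss to the maintenance endpoint. Section 6.6 claims no power for maintenance. Its denominator is also unsettled: section 1.0 restricts it to subjects normothermic by 4 hours who continue cooling, while section 13.0 defines the population circularly, by maintenance itself, and counts from 37°C where its own criterion uses 37.5°C.
- A reader might conclude that the single-nostril cohort is exempt from the 75% criteria. Section 13.0 says only that it is analysed separately; the exemption is for the sponsor to state.

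**Conclusion.** The plan is wrong as written. Section 6.6 requires 25 completers, while section 13.0 permits at most 20 subjects in any one analysis. Set against the stated 80.1%, the best available power on the printed formula is 74.6%; with 0.75 as the null the exact figures are 76.4% and 67.7%. The shortfall in numbers needs no assumption beyond the two sections. The power figures rest on the plan's 90% and 75% and a one-sided 10% level, and the figure for 17 completers also rests on the assumed proportional loss.

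The error concerns the stated size, power and precision. The documents do not support saying that the trial is materially less likely to meet its own success rule. It should be fixed, because it is certain and needs only wording to correct.

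**What to change.** - In sections 6.6 and 13.0, state which cohort the 75% hypotheses apply to. The double-nostril cohort is the natural choice, given the purpose section 13.0 gives the other.
- Replace the claim of 25 subjects and 80% power with the expected exact 90% interval precision at n = 20, for example width 0.33 at 16/20 and 0.26 at 18/20. Alternatively, restate the power at 20 and say plainly that it is not a second success rule, since 18/20 from an exact test would otherwise compete with the 15/20 implied by section 6.3.
- Reconcile the maintenance populations of sections 1.0 and 13.0 before stating a denominator for that endpoint.
- Report the single-nostril cohort (N = 10) separately with its own exact intervals, for example width 0.47 at 8/10.

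Cost: wording changes and a protocol amendment, which section 14.15 says needs FDA approval before use. No extra subjects are needed. The stated power becomes less favourable or gives way to a precision statement.

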6.3 Primary Efficacy Endpoint and Success Criteria

This feasibility study should confirm that the COOLSTAT system has the ability to safely and adequately achieve and maintain normothermic cooling therapy with its control system over a specified period for subjects who were enrolled in the study.

This cooling aspect of the trial will be considered a success if at least 75% of the subjects achieve the following criteria:

- Cooling Performance: The subjects reach normothermia (core temperature $\leq 37.5^{\circ}\text{C}$) within 4 hours of starting COOLSTAT cooling.
- Temperature Maintenance: The subjects are held within a 1.5°C temperature band, between $36^{\circ}\text{C} - 37.5^{\circ}\text{C}$, for 80% of the steady state time following the initial achievement of 37.5°C .³

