13.1 Primary Performance Outcome Analysis

The primary hypothesis regarding cooling performance is that at least 75% of the subjects will reach normothermia (core temperature $\leq 37.5^{\circ}\text{C}$) within 4 hours of starting COOLSTAT cooling.

The primary hypothesis regarding temperature maintenance is that at least 75% of the subjects' core temperatures remain between 36 °C and 37.5 °C for 80% of the steady state time following the initial achievement of 37.5 C.

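### One 75% success verdict is stated for all subjects, but the two airflow groups may not be merged and no rule says which group decides or how a split result is read

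*Combined protocol and SAP*

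**What the plan says.** Section 6.3 gives one verdict for the trial: "This cooling aspect of the trial will be considered a success if at least 75% of the subjects achieve the following criteria". The criteria are core temperature at or below 37.5 °C within 4 hours, and 36 to 37.5 °C for 80% of steady-state time afterwards. Section 13.1 repeats them as primary hypotheses: "The primary hypothesis regarding cooling performance is that at least 75% of the subjects will reach normothermia" within 4 hours, and likewise for maintenance. Section 13.0 describes the comparison: "The proportion of subjects fulfilling success criteria and 90% confidence intervals will be reported and compared to the a priori minimum acceptable criteria". None of these statements, nor the matching ones in the section 1.0 summary, names an airflow group.

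Section 13.0 then sets up two groups. "Subjects 1 through 20 will be assigned to the double nostril air flow treatment group" and "Subjects 21 through 30 will be assigned to the single nostril air flow treatment group". On combining them it says "Double nostril air flow and single nostril air flow subjects will not be merged or directly compared", and then that "The results from subjects treated with single nostril flow will be analyzed separately from subjects treated with double nostril air flow".

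On the role of the second group it says only: "The purpose of this cohort is to assess the safety of and optimal dose for the single nostril air flow configuration of the CoolStat". Within section 13.0, the word exploratory is attached only to the stroke subgroups.

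**The concern.** The natural reading of section 6.3 is one proportion over all treated subjects. Section 13.0 rules that out, so the success statement cannot be carried out as written. Two proportions will exist, each can be set against 75%, and nothing says how they become one verdict.

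Split results are easy to produce. With 14/20 and 8/10, double nostril is at 70% and single nostril at 80%. With 15/20 and 7/10, it is 75% and 70%. In either case the plan gives no answer to whether the cooling aspect of the trial succeeded. Whoever writes the report could settle the rule after seeing which group did better. Section 14.16 foresees using the data in premarket notifications and publications, so the verdict may be relied on outside this trial.

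**Working it through.** **The plan's own figure.** Section 6.6 sizes one group, with proportions 0.90 and 0.75, z = 1.28 and z = 0.84:

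n = [(1.28 × √(0.9 × 0.1) + 0.84 × √(0.75 × 0.25)) / 0.15]² = [(0.384 + 0.364) / 0.15]² = 24.85, rounded up to 25, with 30 treated to allow for dropouts.

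This reproduces. It assumes a single analysis set; under section 13.0 the sets are 20 and 10, and neither reaches 25.

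**Inputs.** Group sizes of 20 and 10 (section 13.0). The 75% criterion read as an observed proportion: at least 15/20, and at least 8/10. Section 6.10 itself uses 8 of 10 to represent 75% in the first 10 subjects.

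**Assumptions (not in the documents).** Groups independent, same true rate p in both, all 20 and 10 evaluable, one criterion at a time.

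**Formulas.** D = P(X ≥ 15 | 20, p) and S = P(X ≥ 8 | 10, p). Both must pass: D × S. Either suffices: 1 − (1 − D)(1 − S). Groups disagree: D(1 − S) + S(1 − D).

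| True rate | D (double alone) | S (single alone) | Both | Either | Disagree |
|---|---|---|---|---|---|
| 0.60 | 12.6% | 16.7% | 2.1% | 27.2% | 25.1% |
| 0.65 | 24.5% | 26.2% | 6.4% | 44.3% | 37.9% |
| 0.70 | 41.6% | 38.3% | 15.9% | 64.0% | 48.0% |
| 0.75 | 61.7% | 52.6% | 32.4% | 81.8% | 49.4% |

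Worked at 0.70: both = 0.416 × 0.383 = 0.159; either = 1 − 0.584 × 0.617 = 0.640.

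**With the section 6.10 condition.** The move to 24-hour cooling needs 8 of the first 10 subjects to meet each criterion. Subjects 21-30 are planned for 24 hours, so their cohort as designed presupposes that this was met, and those first 10 are half of the double-nostril group. Let K be the number of successes among subjects 1-10. At p = 0.70:

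- P(K ≥ 8) = 0.383.
- Double nostril passes as well: the sum over k = 8, 9, 10 of P(K = k) × P(at least 15 − k of the next 10) = 0.281.
- Either suffices: 0.281 + (0.383 − 0.281) × 0.383 = 0.320, a ratio of 0.320/0.281 = 1.14.
- Both must pass: 0.281 × 0.383 = 0.108.

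Double alone against either is 7.7% v 9.2% at 0.60 (1.20 times) and 15.7% v 18.4% at 0.65 (1.17 times).

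**If the 90% confidence limit decides.** Section 13.0 names neither the interval method nor whether the limit or the point estimate decides. With a two-sided exact interval, 10/10 has a lower limit of 0.05^(1/10) = 0.741, below 0.75, so single nostril can never clear the criterion. Double nostril needs 19/20 (lower limit 0.784). Under that rule, either-suffices is the same as double nostril alone, and both-must-pass can never succeed. A Wilson interval gives 0.787 at 10/10, which would clear.

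**The case against.** The strongest reply is that section 13.0 gives the single-nostril cohort a safety and dose purpose, and that section 6.8 calls the whole trial exploratory. On that view the sponsor plainly means double nostril to decide. This shows likely intent but does not write the rule: the cohort is not removed from the primary hypotheses, optimal dose is not defined and could include cooling performance, and subjects 1-20 are nowhere named as the deciding set. A trial that calls itself exploratory but states primary hypotheses and a success criterion still needs that criterion to be executable.

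A reader might go further and infer that the plan grants two chances of success, raising the chance of a favourable verdict by 1.5 times (64.0/41.6 at a true 70%) to 2.2 times (27.2/12.6 at 60%). The documents do not support that:

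- No section says one group is enough. Requiring both is equally open and pushes the other way: 6.4% against 24.5% for double nostril alone at a true 65%. It is also possible to read section 13.0 as giving each configuration its own result, with no shared claim.
- Once the section 6.10 condition must be met, the either-group ratio falls to about 1.14-1.20. The documents do not say what happens to later cohorts if that condition fails, so this holds only where the 24-hour plan is reached.
- Equal true rates are an assumption. If single nostril succeeded in 50% and double in 65%, either-suffices would be 28.7% against 24.5% (1.17 times), even without the section 6.10 condition.
- Under the exact two-sided interval there is no second chance at all.

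**Conclusion.** The point holds as an undefined verdict. Sections 6.3, 13.0 and 13.1 state one success rule that section 13.0 makes impossible to apply to all subjects together, and nothing replaces it. At a true rate of 70%, below the stated minimum, the chance of declaring success on one criterion is 16%, 42% or 64% depending only on which unwritten rule is used. With the section 6.10 condition it is 11%, 28% or 32%.

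These figures rest on the observed-proportion reading, equal and independent groups, and full evaluability. They are per criterion: requiring both criteria lowers them, and the section 1.0 summary limits the maintenance analysis to subjects normothermic by 4 hours, so its denominators are smaller. The size of any inflation cannot be fixed from the documents, nor even its direction. What can be said is that the choice is open after the data are seen. It should be corrected; it does not invalidate the data collected.

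**What to change.** In sections 6.3, 13.0 and 13.1, and in the matching text of section 1.0, state that the primary hypotheses and both 75% criteria are judged in the double-nostril group (subjects 1-20). Label the cooling and maintenance results of the single-nostril group (subjects 21-30) exploratory, and report them as counts with exact 90% confidence intervals and no success or failure verdict against 75%. This follows the purpose that section 13.0 already gives that cohort and removes the split-result problem.

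The cost is a few sentences, with no added subjects or data. The downside is that the sponsor gives up a formal success claim for single-nostril flow, which 10 subjects spread over up to three flow rates could hardly support. If the sponsor wants single nostril to count, the plan must instead state in advance whether both groups must pass and how a split result is read.

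### Section 13.0 appears to combine 8-hour and 24-hour double-nostril subjects in one maintenance rate, which then cannot support a statement about 24-hour maintenance

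*Combined protocol and SAP*

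**What the plan says.** Section 13.0 states "Subjects 1 through 20 will be assigned to the double nostril air flow treatment group". Within that group it lists two lines: "Subjects 1 through 10 will be treated for 8 hours (N=10" and "Subjects 11 through 20 will be treated for 24 hours (N=10". A third set of ten, subjects 21 to 30, also receives 24 hours but with single-nostril flow, and is kept apart: "Double nostril air flow and single nostril air flow subjects will not be merged or directly compared".

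Section 6.3 sets the success rule: "This cooling aspect of the trial will be considered a success if at least 75% of the subjects achieve the following criteria". For maintenance, a subject must stay between 36 °C and 37.5 °C "for 80% of the steady state time following the initial achievement of" 37.5 °C (Section 13.0). No fixed observation window is given, so each subject is scored over his or her own steady-state time.

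The only subgroup analysis named is by stroke type: "An exploratory analysis of participant subgroups will be performed, stratified by stroke presentation (ischemic versus hemorrhagic"). Treatment duration is not mentioned there. The only duration-specific rule is in Section 6.10, where 8 of the first 10 subjects must meet the maintenance criterion, among other conditions, before later subjects move to 24-hour cooling.

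**The concern.** A maintenance success in subjects 1 to 10 and one in subjects 11 to 20 are not the same event. The first group is never observed on the device past hour 8, so it carries no information on control in the last 16 hours of a 24-hour treatment. If both groups enter one proportion, half the weight of that proportion comes from subjects who could neither show nor fail to show 24-hour maintenance.

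The final report goes to FDA, and Section 14.16 allows the data to support later premarket notifications. A single figure at or above 75% for double-nostril flow could then be read as evidence of 24-hour maintenance when the 24-hour subjects themselves fell short of 75%.

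**Working it through.** **Inputs.** Threshold 75% of subjects (6.3, 13.0); 10 subjects at 8 h and 10 at 24 h in the double-nostril group (13.0); gate of 8/10 on the 8-hour subjects (6.10); 4-hour limit for reaching 37.5 °C (6.3, 13.0); 90% CI reported and compared with the criterion (13.0).

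**1. The plan's own figures.** The gate follows from the threshold: 0.75 × 10 = 7.5, rounded up to 8, as 6.10 states. The sample size in 6.6 also reproduces: [(1.28 × √(0.9 × 0.1) + 0.84 × √(0.75 × 0.25)) / 0.15]² = [(0.384 + 0.364) / 0.15]² = 24.8, rounded up to 25. That figure is not in dispute here; it takes no account of duration.

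**2. Scoring windows.** For an uninterrupted completer who reaches 37.5 °C at time t, with t greater than 0 and at most 4 h, the window is treatment length minus t.
- 8-hour subjects: at least 8 − 4 = 4 h, under 8 h.
- 24-hour subjects: at least 24 − 4 = 20 h, under 24 h.

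The two ranges do not overlap.

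**3. What the combined mark asks of subjects 11 to 20.** With all 20 evaluable, the mark is 0.75 × 20 = 15 successes. The gate leaves 8, 9 or 10 successes among subjects 1 to 10.

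| Successes, subjects 1–10 | Needed, subjects 11–20 | Rate at 24 h |
|---|---|---|
| 8/10 | 15 − 8 = 7 | 70% |
| 9/10 | 15 − 9 = 6 | 60% |
| 10/10 | 15 − 10 = 5 | 50% |

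Every row is below 75%. The same threshold applied to subjects 11 to 20 alone would need 8/10.

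**4. Fewer evaluable subjects.** The synopsis limits the maintenance population to subjects normothermic by 4 hours who continue cooling. With 8 to 10 evaluable at 8 h (all succeeding) and 7 to 10 at 24 h, the minimum 24-hour rate runs from 43% (3/7) to 60% (6/10).

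**5. Illustration under assumed true rates.** These rates are not in the documents. Let A ~ Bin(10, p8) and B ~ Bin(10, p24). Then P(pass) = Σ P(A = a) × P(B ≥ 15 − a). With p24 = 0.60:

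| Assumed p8 | Combined rule passes |
|---|---|
| 0.80 | 41% |
| 0.90 | 62% |
| 0.95 | 73% |
| 1.00 | 83% |

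These figures do not condition on passing the gate. Conditioning raises the first row most: P(A ≥ 8 and pass) / P(A ≥ 8) = 0.375 / 0.678 = 55%. For comparison, P(B ≥ 8) = 17% at p24 = 0.60. That comparator is a stricter cut, 80% at N = 10, and passes only 53% of the time when the true rate is exactly 75%.

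**6. Precision.** Exact (Clopper-Pearson) 90% intervals: 15/20 gives 54% to 90%; 8/10 gives 49% to 96%.

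**The case against.** Several objections have force.

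- **Pooling is implied, not stated.** A reader might infer that the SAP explicitly combines the durations. No sentence does so, and Section 13.0 lists the 8-hour and 24-hour subjects on separate lines. What stands is the plain reading of one group under one criterion, with separation specified for nostril configuration and for nothing else.
- **The first ten are scored separately.** Section 6.10 requires it. If a rate for all 20 is published, the result for subjects 11 to 20 follows by subtraction. Section 13.0 also plans plots of core temperature, so late loss of control would not be invisible. But the gate tests nothing beyond hour 8, and a result obtainable by subtraction is not a planned analysis with an interval.
- **The interval might protect.** A rule that the lower 90% limit exceed 75% would need 19/20, and 15/20 would fail. Section 13.0 says only that the interval is reported and compared; Section 6.3 is a point-estimate rule.
- **Longer treatment need not mean lower success.** A reader might infer that control is worse at 24 hours. The documents do not show this. The criterion is a share of time: 20% of 4 h allows 48 minutes out of range, while 20% of 20 h allows 4 hours. One short breakthrough fever could fail an 8-hour subject and not a 24-hour one. Section 5.5.2 also reports that temperature was held in 24-hour pig tests.
- **This is a feasibility study.** Its hypothesis makes no explicit 24-hour claim, and ten subjects give a wide interval. That limits the weight of the point. It does not make a rate over non-overlapping windows easier to interpret.

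**Conclusion.** The point holds as a limit on what the combined maintenance rate can show. Given the 6.10 gate, the point-estimate rule of 6.3 and all 20 subjects evaluable, the combined criterion is met with 5 to 7 of 10 among subjects 11 to 20, always below the study's own 75%. The rate therefore cannot support a statement about 24-hour maintenance with double-nostril flow.

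A reader might go further and say that the criterion passes when only half of the 24-hour subjects hold temperature. That is the extreme case: all ten 8-hour subjects must succeed. At the assumed 90% rate used in 6.6, that has probability 0.9¹⁰ = 0.35. At the gate minimum the figure is 70%. Nor does it describe every subject treated for 24 hours, since subjects 21 to 30 are analysed separately.

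The 41% to 83% range, against 17%, depends on assumed rates and on a stricter comparator. It shows that the choice of analysis matters, not what this trial will find. The direction of any difference between 8 and 24 hours is unknown.

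**What to change.** In Section 13.0, specify two maintenance results for double-nostril flow, each with its 90% CI:

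- (a) over a common window, from the start of cooling to hour 8, for all evaluable subjects among 1 to 20, scoring the steady-state time that falls within it;
- (b) over the full treatment period, for subjects 11 to 20 alone.

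Add that any statement about 24-hour maintenance with double-nostril flow rests on (b).

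The cost is SAP wording and one extra table. Section 12.6 has the device logging core temperature every second, so no new data, subjects or procedures are needed. The downside is precision: (b) rests on at most 10 subjects, and even 8/10 has an exact 90% lower limit of 49%. Reporting that openly is preferable to narrowing the interval with subjects not cooled past hour 8. Label: cheap improvement.
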